5.1. Criteria for inclusion of subjects

1. Male and female patients aged 40 to 75 years.
2. Availability of the Informed Consent Form signed by the patient (or his/her legal representative if the patient is not physically able to sign) for participation in the trial.
3. First-time diagnosed hemispheric ischaemic stroke (ICD-10 codes: I63 "cerebral infarction." I63.0 to I63.9) not more than 48 hours old.
4. Presence of neuroimaging (according to computerised tomography (CT) or magnetic resonance imaging (MRI)) signs of ischaemic stroke and/or absence of signs of haemorrhagic stroke, ischaemic stroke with haemorrhagic impregnation, as well as other conditions not related to ischaemic stroke and having a similar clinical picture.
5. Assessment of the patient's functional status using the Modified Rankin Scale (mRS) 3 or more points).
6. Patient's NIHSS score of 9 to 15 points inclusive.
7. Negative pregnancy test in female patients of preserved childbearing potential.
8. Consent to the use of adequate contraceptive methods (contraceptive methods with a reliability of more than 90%: non-hormonal intrauterine device; condom with intravaginal spermicide; neck caps with spermicide; diaphragms with spermicide), or complete abstinence from sexual activity for the period of the trial.
9. Patients who are able to understand the requirements of the Trial Protocol and who have consented to all restrictions in the Trial Protocol.

5.2. Criteria for non-inclusion of subjects

1. Presence of clinically significant allergic reactions in the history.
2. Hypersensitivity and/or intolerance to any component of the investigational product or placebo.
3. Presence of lactose intolerance/congenital galactose intolerance; Lapp lactase deficiency or glucose-galactose malabsorption syndrome.
4. BMI value > 35.
5. Recurrent stroke.
6. Haemorrhagic stroke (confirmed by neuroimaging (CT or MRI)).
7. Haemorrhagic infarction (ischaemic stroke with haemorrhagic impregnation).
8. Parkinson's disease or parkinsonism.
9. Multiple sclerosis.
10. Uncontrolled epilepsy.

11. Demyelinating diseases of the nervous system.
12. Hereditary degenerative diseases of the CNS.
13. Presence of infectious diseases of the CNS in the anamnesis.
14. Traumatic brain injuries with pronounced neurological symptoms and cognitive impairment.
15. A history of neurodevelopmental anomalies or other neurological disorders seriously affecting motor or cognitive function in the reasonable opinion of the investigator.
16. Patients who have undergone thrombolytic therapy or thrombectomy.
17. Need for surgical intervention.
18. Evidence of a first-diagnosed disease that, in the reasonable opinion of the investigating physician, would preclude the patient's participation in the trial.
19. Evidence of a significant uncontrolled comorbid condition that, in the reasonable opinion of the investigator, would preclude the patient's participation in the trial, including:
 - Respiratory system disorders;
 - Cardiovascular disorders including SBP \geq 200 mmHg, DBP \geq 100 mmHg at trial entry;
 - Severe renal impairment (eGFR $<$ 30 ml/min/1.73 m²);
 - Severe liver function impairment (ALT, AST activity $>$ 2 times ULN);
 - Endocrine disorders;
 - Gastrointestinal disorders.
 - Deep vein thrombosis or pulmonary embolism, identification of a floating thrombus.
 - The onset of a seizure syndrome.
 - Occurrence of unrelieved hyperthermia.
 - Occurrence of unrelieved hyperglycaemia.
20. Endogenous psychiatric disorders according to anamnesis.
21. Anamnestic information about dementia of the Alzheimer type.
22. Systemic autoimmune diseases or vascular collagenosis requiring previous or current treatment with systemic corticosteroid drugs, cytostatics; malignant neoplasms within the last 5 years.
23. A history of alcohol or drug dependence.
24. Pregnancy or lactation period.
25. The need to use medications that are prohibited in this trial.
26. Administration of unauthorized or off-protocol medications within 2 weeks prior to trial inclusion (except for a single administration of ethylmethylhydroxypyridine succinate at the emergency medical services stage).
27. Positive result of at least one of the following tests: blood tests for HIV, syphilis, hepatitis B and C (including history).
28. Presence of any significant history in the opinion of the investigator, condition that prevents the patient from being included in the trial.
29. Participation in any clinical trial less than 3 months prior to the start of the trial.
30. Positive result of a rapid test for IgM antibodies to SARS-CoV-2 virus.

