Extremely severe course - in the initial dosage of 800 mg/day until persistent relief of manifestations of pancreatogenic shock, after stabilisation of the condition 300 - 500 mg BID by IV drip (in 0.9% sodium chloride solution) with gradual reduction of daily dosage.

Contraindications

Acute liver and kidney dysfunction, hypersensitivity to the drug. Strictly controlled clinical studies of safety of use of Mexidol in children, during pregnancy and lactation have not been conducted.

Side effects

To avoid side effects, it is recommended to observe the dosing regime and the rate of drug administration.

The frequency of side effects was determined according to the World Health Organisation (WHO) classification:

very frequent ($\geq 10\%$); frequent ($\geq 1\%$, but $< 10\%$); infrequent ($\geq 0.1\%$, but $< 1\%$); rare ($\geq 0.01\%$, but $< 0.1\%$); very rare ($< 0.01\%$); frequency unknown (frequency cannot be determined based on available data).

Immune system disorders: very rare - anaphylactic shock, angioedema, urticaria.

Mental disorders: very rare - somnolence.

Nervous system disorders: very rare - headache, dizziness (may be associated with excessively high rate of administration and is of short-term nature).

Vascular disorders: very rare - decrease in BP, increase in BP (may be associated with excessively high rate of administration and is transient).

Respiratory system, chest and mediastinal organs: very rare - dry cough, sore throat, chest discomfort, breathing difficulties (may be associated with excessively high rate of administration and is of short-term nature).

Gastrointestinal disorders: very rare - dry mouth, nausea, unpleasant odour, metallic taste in the mouth.

Skin and subcutaneous tissue disorders: very rare - pruritus, rash, hyperaemia.

General disorders and administration site reactions: very rare - sensation of warmth.

Interaction

It increases the effect of benzodiazepine anxiolytics, anticonvulsants (carbamazepine), antiparkinsonian agents (levodopa). It reduces the toxic effects of ethyl alcohol.

Special precautions

In individual cases, especially in predisposed patients with bronchial asthma with hypersensitivity to sulfites, the development of severe hypersensitivity reactions and bronchospasm is possible.

Overdose

Symptoms: drowsiness, insomnia.

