Special patient groups

Children

Safety and efficacy of Mexidol FORTE 250 in children aged 0 to 18 years have not been established.

Method of administration:

Per os.

Contraindications

- acute liver and kidney dysfunction,
- hypersensitivity to ethylmethylhydroxypyridine succinate or to any of the excipients.
- infancy (due to insufficiently studied effect of the drug);
- pregnancy, breastfeeding (due to insufficient trial of the drug action);
- lactose intolerance, lactase deficiency, glucose-galactose malabsorption.

Special instructions and precautions for use

Patients with rare hereditary fructose intolerance, galactose intolerance, galactosemia or glucose-galactose malabsorption should not take this preparation.

Fertility, pregnancy and lactation

Mexidol FORTE 250 is contraindicated in pregnancy and during breastfeeding.

Side effects

Summary of adverse reactions

The frequency of side effects was determined according to the World Health Organisation (WHO) classification:

very frequent ($\geq 10\%$); frequent ($\geq 1\%$, but $< 10\%$); infrequent ($\geq 0.1\%$, but $< 1\%$); rare ($\geq 0.01\%$, but $< 0.1\%$); very rare ($< 0.01\%$); frequency unknown (frequency cannot be determined based on available data).

Immune system disorders: very rare - angioedema, urticaria.

Mental disorders: very rare - somnolence.

Nervous system disorders: very rare - headache.

Gastrointestinal disorders: very rare - dry mouth, nausea, pain, burning and discomfort in the epigastric region, heartburn, flatulence, diarrhoea.

Skin and subcutaneous tissue disorders: very rare - rash, pruritus, hyperaemia.

Suspected adverse reactions reporting

It is important to report suspected adverse reactions after registration of the medicinal product in order to ensure continuous monitoring of the benefit-risk ratio of the medicinal product. Healthcare professionals are encouraged to report any suspected adverse drug reactions through the national adverse reaction reporting systems of the Eurasian Economic Union member states.

Russian Federation

Address: [name]

Federal Service for Surveillance in Healthcare

[contact], [contact]

Email: [contact]

Site <http://www.roszdravnadzor.ru/>

Overdose

Symptoms

Drowsiness, insomnia.

Treatment

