All patients with preserved reproductive potential should have a negative pregnancy test result. It is planned to use CT/MRI data performed within 48 hours prior to inclusion of the patient in the trial to confirm the underlying diagnosis. The patient is assessed using questionnaires (mRS, NIHSS). The investigator collects information about the patient's medical history, previous and current therapy, and assesses the patient's eligibility. If data are available for a patient from instrumental examinations performed within 48 hours prior to inclusion in the trial, they can be used to assess the patient's condition and eligibility for inclusion/non-inclusion. The use of such data shall be permitted only if the data are available in full and for all parameters required by the Protocol. The results of the examination are recorded in the patients' CRF. Based on the results of the examinations, the investigator makes a conclusion, based on which the patient is allowed or not allowed to participate further in the trial (Visit 1).

Thus, the following procedures are provided at this stage:

- Signing an informed consent form;
- Collection of demographic and anthropometric data, anamnesis;
- Physical examination
- Neurological examination;
- Assessment of vital signs (BP, HR, RR, body temperature);
- Clinical blood test;
- Blood chemistry;
- Blood tests for HIV, Syphilis, Hepatitis B and C (results obtained within 48 hours prior to Screening can be used);
- Urinalysis;
- Pregnancy test for women with preserved reproductive potential;

- ECG¹;
- Completion of specialized scales (mRS, NIHSS);
- CT/MRI²;
- Assessment of prior and concomitant therapy;
- Assessment of inclusion/non-inclusion criteria

Randomization and initiation of therapy

Visit 1

Randomization is performed for patients who meet inclusion criteria and do not have non-inclusion criteria. In the subpopulation of patients involved in the evaluation of the pharmacodynamic effects of the investigational therapy, blood samples are collected for the trial of pharmacodynamic effects. According to the randomization number, the patient is assigned to the investigational therapy. The prescribed therapy is started.

Thus, if the patient fulfils the eligibility criteria, the following procedures are carried out:

- Randomization
- Completion of specialised scales and calculation of indices (HADS, MoCA, Rivermead mobility index);
- Administration and initiation of the investigational therapy
- AE registration

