Therapy period

Visit 2 (day 11/12³ from the start of therapy, Visit procedures are performed at the end of parenteral therapy)

The visit is conducted in the inpatient setting of the investigational site and includes the following procedures:

- physical examination,
- neurological examination,
- assessment of vital signs (BP, HR, respiratory rate, body temperature),
- evaluation of concomitant therapy,
- AEs registration;
- evaluation of exclusion criteria;
- clinical blood test,
- blood chemistry;
- urinalysis;
- ECG
- completion of specialised scales and calculation of indices (mRS, NIHSS, HADS, MoCA, Rivermead mobility index),
- dispensing of oral medication

The investigator decides on the patient's discharge from the hospital, instructs the patient on the rules of the trial, administration of the investigational therapy and planned Visits/procedures.

Telephone visit 1 (Day 24±2 from initiation of therapy; Day 14±2 from initiation of oral therapy).

¹ If data are available for a patient from instrumental examinations performed within 48 hours prior to inclusion in the trial, they can be used to assess the patient's condition and eligibility for inclusion/non-inclusion. The use of such data shall be permitted only if the data are available in full and for all parameters required by the Protocol.

² The plan is to use data from neuroimaging examinations performed within 48 hours prior to patient inclusion in the trial to assess patient status and eligibility for inclusion/non-inclusion. A repeat CT/MRI scan is not required if these findings are present.

³ If the first administration of the investigational product (start of parenteral therapy) falls on the second half of the day (first day of therapy - one administration), Visit 2 is performed on day 12 in the morning.

The investigator should contact the patient by telephone to assess concomitant therapy, to record AE and assess exclusion criteria, and to assess compliance.

Visit 3 (Day 40 (+2) from initiation of therapy; Day 30 (+2) from initiation of oral therapy):

The visit is conducted in the context of the patient's outpatient visit to the investigational site and includes the following procedures:

- physical examination,
- assessment of vital signs (BP, HR, respiratory rate, body temperature),
- evaluation of concomitant therapy,
- AEs registration;
- evaluation of exclusion criteria;
- dispensing/accounting for oral medication,
- compliance assessment

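### Section 2.2 contraindicates both product forms in acute liver and kidney dysfunction, but no non-inclusion criterion names it; acute kidney dysfunction with eGFR of 30 or more is left to investigator judgement

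*Protocol*

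**What the plan says.** **Product information (Protocol section 2.2).** The contraindications for the solution open with "Acute liver and kidney dysfunction, hypersensitivity to the drug". The list for the FORTE 250 tablets also includes "acute liver and kidney dysfunction". Neither entry carries a severity grade or a laboratory threshold.

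**Eligibility (Protocol section 5.2; criterion 19 is the same in the synopsis).** Criterion 19 concerns significant uncontrolled comorbidity that the investigator thinks should bar participation, and gives a list of inclusions. Two bullets set organ limits:
- "Severe renal impairment (eGFR", with the limit below 30 ml/min/1.73 m²;
- "Severe liver function impairment (ALT, AST activity", with the limit above 2 times ULN.

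Two further criteria are general and discretionary:
- criterion 18: "Evidence of a first-diagnosed disease that, in the reasonable opinion of the investigating physician, would preclude the patient's participation in the trial";
- criterion 28: "Presence of any significant history in the opinion of the investigator, condition that prevents the patient from being included in the trial".

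**Entry to the trial (Protocol section 6.2, Visit 1).** "Randomization is performed for patients who meet inclusion criteria and do not have non-inclusion criteria". Section 4.3.2 and the Visit 0 text in section 6.2 add that the investigator decides, after the screening results, whether the patient may go on.

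**Monitoring (Protocol sections 6.2 and 6.3.8).** Chemistry is scheduled at Visits 0, 2 and 4. For Visit 2, "Visit procedures are performed at the end of parenteral therapy".

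**The concern.** A labelled contraindication would normally appear as a non-inclusion criterion. Here the product section says the drug should not be given in acute liver or kidney dysfunction, while the eligibility list mentions only impairment it calls severe. A reader of section 5.2 alone could take the renal cut-off to mean that an eGFR of 30 or more is acceptable, acute or not.

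The stake is patient safety and consistency within the protocol. Section 2.4.2 presents subject selection as one of the safety measures. Section 2.2 describes excretion mainly in urine and, for the tablets, metabolism in the liver. The regimen is also heavier than in EPICA: 1000 against 500 mg/day IV, and 750 against 3 × 125 = 375 mg/day orally. If an investigator did not regard the acute dysfunction as a bar, enrolment would breach no listed criterion. The monitor's check of selection criteria (section 11.3) need not then flag it.

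**Working it through.** The plan gives no figure to reproduce on this point. The check compares texts. Two readings are assumed: the contraindication applies to either organ, and the two numeric limits in criterion 19 exclude automatically, although its lead-in refers to investigator opinion.

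**Step 1. Tablet contraindications (section 2.2) against the eligibility criteria (sections 5.1 and 5.2).**

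| Contraindication | Where it is carried over |
|---|---|
| Hypersensitivity | Non-inclusion 2 |
| Infancy | Inclusion 1 (40 to 75 years) |
| Pregnancy, breastfeeding | Non-inclusion 24 |
| Lactose, lactase and glucose-galactose disorders | Non-inclusion 3 |
| Acute liver and kidney dysfunction | Not named; partly covered by the criterion 19 limits |

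Four of five are named. This counts labels, not risk. Its use is to show that the remaining item looks like an omission.

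**Step 2. What the set limits catch.**

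| Acute dysfunction | Set limit met? | Other named cover |
|---|---|---|
| Kidney, eGFR < 30 | Yes, criterion 19 | – |
| Kidney, eGFR ≥ 30 | No | None |
| Liver, ALT/AST > 2 × ULN | Yes, criterion 19 | Criteria 23 and 27 where they apply |
| Liver, ALT/AST ≤ 2 × ULN | No | Criterion 23 (alcohol or drug dependence) and criterion 27 (hepatitis B or C, including history) |

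The second row is the real gap. The fourth is close to nominal, because the transaminase limit is low and two common routes to liver disease are excluded by name.

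**Step 3. What keeps the second-row patient out.** Only judgement: criterion 18 if the condition is newly diagnosed, the open list in criterion 19, criterion 28, and the investigator's decision in sections 4.3.2 and 6.2. None names the kidney at this level of function or refers back to section 2.2. The withdrawal criteria in section 5.3 do not name the condition either.

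**Step 4. Scheduled exposure before the next scheduled chemistry.** Inputs are 20 administrations (Appendix 1 footnote on the start of therapy) and 500 mg each (section 2.2):

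20 × 500 mg = 10,000 mg IV.

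This is what the schedule provides for in the active group if nobody tests or acts earlier. It is not a forecast.

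**Step 5. How many patients.** The documents give no frequency of acute kidney dysfunction at screening and no pre-stroke kidney function, so the number cannot be calculated.

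**The case against.** The best defence is that the means to exclude already exist. Criterion 19 is open-ended, its bullets being examples. Criterion 18 fits newly found kidney dysfunction. The investigator decides with Visit 0 creatinine, ALT and AST in hand and with the contraindication printed in the same protocol. A careful investigator would probably refuse the patient. This stands, and it limits the weight of the point. It does not remove it, because each route asks whether the condition should bar the patient, which a contraindication has already answered.

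Three stronger readings are tempting and are not supported:

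- *That the liver is as exposed as the kidney.* The ALT/AST limit and criteria 23 and 27 cover most of that side.
- *That an affected patient would inevitably receive all 20 infusions.* This follows only from the scheduled chemistry. Patients are inpatients during this period. Section 6.3.8 allows extra laboratory work, sections 6.1 and 6.2 allow extra visits, and section 8.3 treats new or worsening laboratory abnormalities as adverse events. Withdrawal criteria 3 and 5 can act at any time. On the other side, Appendix 1 first schedules the exclusion-criteria check at Visit 2.
- *That the gap can be sized as a percentage loss of eGFR.* That needs a pre-stroke eGFR, which the documents do not give, so any such figure would only restate an assumed baseline.

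The described pharmacology also tempers the risk. Section 2.2 reports low toxicity and, for the IV route, little excretion of unchanged drug. It does mention a pharmacologically active metabolite detected in urine. The IV dose of 1000 mg/day is below the stated maximum of 1200 mg, and the oral dose of 750 mg/day equals its maximum.

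**Conclusion.** The point holds, as a minor one. The eligibility list does not carry over a contraindication that section 2.2 states for both product forms. The practical gap is acute kidney dysfunction with an eGFR of 30 or more, which meets no set limit and is kept out only by investigator judgement.

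The number of patients affected is unknown and probably small. No effect on efficacy, sample size or error rates is claimed. The conclusion rests on the two readings stated in the working. If the criterion 19 limits were instead discretionary, the gap would be wider. Confidence is medium: the textual facts are plain, but the practical consequence depends on how investigators use their discretion.

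**What to change.** Add one non-inclusion criterion to section 5.2 and the synopsis, for example: *Acute kidney or liver dysfunction (contraindication per section 2.2), as judged by the investigator from Visit 0 creatinine, ALT, AST, any available earlier values and history, regardless of the eGFR or ALT/AST value.* Keep the limits of eGFR < 30 and ALT/AST > 2 × ULN.

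The investigator would still judge whether acute dysfunction is present, but no longer whether it excludes the patient.

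The cost is amendment wording. Creatinine, ALT and AST (section 6.3.8) and medical history (section 6.3.2) are already collected at Visit 0, so no new test is needed. The downsides are a few more screen failures and a residual uncertainty: no pre-stroke creatinine is required, so telling acute from chronic impairment remains the investigator's call.

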When administered intravenously, it is determined in blood plasma for 4 h after administration. Time to reach maximum concentration Tmax is 0.45-0.5 h. Cmax at administration of 400-500 mg dose is 3.5-4.0 µg/ml. Mexidol® is rapidly transferred from the bloodstream to organs and tissues and rapidly eliminated from the body. The mean retention time (MRT) is 0.7-1.3 h. The drug is excreted mainly with urine, mainly in glucuron-conjugated form and in insignificant amounts in unchanged form.

Indications for use:

acute cerebral circulatory disorders;
craniocerebral trauma, consequences of craniocerebral injuries;
dyscirculatory encephalopathy;
autonomic dystonia syndrome;
mild cognitive disorders of atherosclerotic genesis;

anxiety disorders in neurotic and neurosis-like states;
acute myocardial infarction (from the first day) as part of complex therapy;
primary open-angle glaucoma of various stages, as part of complex therapy;
management of withdrawal syndrome in alcoholism with predominance of neurosis-like and vegetative-vascular disorders;
acute intoxication with antipsychotic drugs;
acute purulent-inflammatory processes of the abdominal cavity (acute necrotising pancreatitis, peritonitis) as part of complex therapy.

Method of application and doses (according to the IMU):

IM or IV (bolus or drip). In infusion method of administration the drug should be diluted in 0.9% sodium chloride solution.

Mexitol® is administered slowly over 5-7 min, drip - at a rate of 40-60 drops per minute. The maximum daily dose should not exceed 1200 mg.

In acute cerebral circulatory disorders Mexidot® is used in the first 10-14 days - IV drip 200-500 mg 2-4 times a day, then IM 200-250 mg 2-3 times a day for 2 weeks.

In craniocerebral trauma and consequences of craniocerebral traumas Mexidot® is used during 10 - 15 days by IV drip 200 - 500 mg 2 - 4 times a day.

In dyscirculatory encephalopathy in decompensation phase Mexidot® should be administered by IV bolus or drip in a dose of 200 - 500 mg 1 - 2 times a day for 14 days. Then 100 - 250 mg/day IM for the next 2 weeks.

For course prophylaxis of dyscirculatory encephalopathy the drug is administered IM in a dose of 200 - 250 mg BID for 10 - 14 days.

In mild cognitive disorders in elderly patients and in anxiety disorders the drug is administered IM in a daily dose of 100 - 300 mg/day for 14 - 30 days.

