Treatment: due to low toxicity, overdose is unlikely. Treatment is usually not required - symptoms disappear on their own within 24 hours. In severe manifestations, supportive and symptomatic treatment is carried out.

Use in pregnancy and during breastfeeding:

Mexitol® is contraindicated in pregnancy and during breastfeeding.

Effect of the IP on the ability to drive vehicles or operate mechanisms:

During the period of IP administration, caution should be exercised in work requiring quick psychophysical reactions (driving vehicles, mechanisms, etc.).

Within the framework of the present clinical trial it is planned to use Mexidol® solution for

intravenous and intramuscular administration, 50 mg/ml (Pharmasoft, Russia) 10 ml (500 mg) BID (1000 mg per day) by intravenous drip in 100-200 ml of 0.9% NaCl solution for 10 days in patients in the acute and early recovery periods of ischaemic stroke against the background of standard therapy.

Mexidol® Forte 250 film-coated tablets, 250 mg

Trade Name:	Mexidol® Forte 250
Group name:	Ethylmethylhydroxypyridine succinate
Marketing Authorization Holder/ Claims Receiving Organisation:	RPC PHARMASOFT LTD Legal address: [name] Postal address: [name] Tel/[contact]
Manufacturer:	ZiO-Zdorovye CJSC, [name] [contact] Mobile [contact]
Dosage form:	Film-coated tablets
Dosage:	250 mg
Composition per 1 tablet:	Composition per 1 tablet: Active ingredient: Ethylmethylhydroxypyridine succinate as 100 % substance - 250.0 mg Excipients: lactose monohydrate, povidone K-30, magnesium stearate. Film coating: Opadry II pink 33G240018 (hypromellose, titanium dioxide, lactose monohydrate, macrogol 4000, triacetin, iron oxide dye red, iron oxide dye yellow)
Description:	Round biconvex tablets covered with light pink film coating. On a transverse section, the nucleus is almost white.
Storage conditions	Store in a place protected from light, out of reach of children, at temperatures not exceeding 25 °C.

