2.3.2. Results of clinical studies

Mexidol® is rapidly absorbed when taken orally, at doses of 400-500 mg Cmax is 3.5-4 mcg/ml. The drug is rapidly distributed in organs and tissues. The average retention time of

ethylmethylhydroxypyridine succinate in the body when administered orally is 4.9-5.2 h; T1/2 is 2-2.6 h. [IMU].

Use of Mexidol® at the pre-hospital stage in the complex therapy of acute cerebral circulatory disorders

The use of Mexidol® at the pre-hospital stage with its subsequent administration in hospital allowed to significantly reduce mortality of patients with various types of ACCD, including hemorrhagic, to achieve faster and more stable regression of neurological symptoms, to improve the subsequent quality of life of patients and the level of their social adaptation. The drug was well tolerated by patients, did not cause significant changes in BP, HR and respiratory rate, no side effects were observed during therapy with Mexidol®. The obtained results allowed to recommend Mexidol® for use at the pre-hospital stage as a means of urgent undifferentiated therapy in emergency conditions in patients with all types of acute disorders of cerebral circulation with subsequent continuation of the drug in hospital [Sidorov A.M. Borisova V.A., 2005].

Use of Mexidol® at the hospital stage in the complex therapy of cerebral circulatory disorders

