According to modern recommendations, treatment of patients who have suffered an ischaemic stroke in the early recovery period should be aimed both at elimination of the existing neurological deficit and prevention of neurological deficits of a recurrent stroke. Therefore, all patients in the trial, including the placebo group, will receive ischaemic stroke therapy according to the Clinical Guidelines for Ischaemic Stroke and Transient Ischaemic Attack in Adults, 2015.

In this clinical trial, patients receive therapy adequate to their status, including their primary and possible comorbidities, in full, with the exception of some drugs prohibited by this protocol.

At the same time, patients in the placebo group do not carry the risks associated with receiving the investigational therapy because the components of the two placebo forms used are inert and their administration (excluding the performance of intravenous injections) is not an invasive procedure.

Thus, for patients in the placebo group, the risk-benefit ratios are balanced and the prescribed therapy is within the limits of available medical care, so the use of placebo in the present trial is ethically acceptable.

Risks associated with diagnostic procedures

The risks associated with diagnostic procedures do not exceed those for routine medical practice.

Other risks taken by patients in connection with participation in a clinical trial are determined by the **experimental nature of the trial**, as the exact outcome is not known.

During the course of the trial, all treatment and diagnostic measures according to the Protocol will be performed at the Sponsor's expense; qualified personnel will participate in the diagnostic examinations. As a result of the examination, patients will receive reliable information about their health status.

Based on the above, it can be concluded that the benefits of patient participation in this clinical trial exceed the risks taken by patients in both groups, which characterises the risk/benefit ratio as ethically acceptable.

2.5. Description and justification of the method of administration, dosage and dosing regimen of investigational products

In accordance with the legal and regulatory framework, the trial will be performed with samples of the investigational product and comparator product provided by the Sponsor.

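### Criterion 26 admits patients given the study substance by the ambulance with no dose limit, minimum interval or counting rule, so a compliant Group I patient can pass the 1200 mg daily maximum quoted in Section 2.2

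*Protocol*

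**What the plan says.** Protocol Section 5.2, criterion 26 (repeated in the synopsis), excludes patients for "Administration of unauthorized or off-protocol medications within 2 weeks prior to trial inclusion", with one exemption: "except for a single administration of ethylmethylhydroxypyridine succinate at the emergency medical services stage". Section 2.2 identifies that substance as the active ingredient of both investigational products.

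The exemption fixes the number of administrations at one. It gives no amount in mg and no minimum time before the first trial infusion, and neither document says how the dose counts towards Day 1. Timing is bounded only indirectly, by inclusion criterion 3 in Section 5.1, under which the stroke must be "not more than 48 hours old".

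On dosing, Section 2.2 sets the trial's parenteral regimen at "10 ml (500 mg) BID (1000 mg per day"). In the extract from the instructions for medical use, the same section states: "The maximum daily dose should not exceed 1200 mg". Its next paragraph gives the regimen for acute cerebral circulatory disorders as "IV drip 200-500 mg 2-4 times a day".

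Section 6.1 allows screening, randomisation and the first infusion on one day. Its footnote on Visit 2 gives a single Day 1 infusion when therapy starts in the second half of the day. A footnote to Appendix 1 sets the parenteral course at 20 infusions over 10 days.

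Medical history at Visit 0 (Section 6.3.2) covers therapy in the preceding four weeks. The SAP randomisation list is blocked within country. Age is the only subgroup that either document names, and neither plans any analysis by pre-hospital exposure.

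**The concern.** Two things are at stake.

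The first is safety. The eligibility rule and the Day 1 schedule were written separately, and nothing joins them. A patient who meets every criterion and is dosed exactly as planned can receive more of the substance in one day than a maximum printed in the same protocol. This is a combination of stated rules, not a protocol deviation, so monitoring for deviations would not pick it up. Treatment is blinded, so the investigator cannot know at the bedside whether the infusions add to the ambulance dose. The wording has to settle the matter beforehand.

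The second is interpretation. Some patients randomised to placebo may have had one dose of the active substance before their baseline mRS and NIHSS scores. No planned table or analysis would show how many, or whether the result depends on them.

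**Working it through.** **Inputs**
- Trial dose, Group I: 2 x 500 mg = 1000 mg per day (Protocol 2.2).
- Quoted daily maximum: 1200 mg (Protocol 2.2, from the instructions for medical use).
- Quoted single dose in acute stroke: 200-500 mg, given 2-4 times a day (same place).
- Ambulance dose: not in the documents. The 200-500 mg range is used here as an assumption.
- Sample-size inputs (Protocol 9.1): ε = 0.292, δ = 0.027, σ = 0.802, one-sided α = 0.05, power 80%.

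**Infusions on Day 1.** The protocol does not state outright that a first-half start means two infusions, but its schedule implies it. Twenty infusions in 10 days is two per day, with Visit 2 on Day 11. Only the second-half start has one infusion on Day 1, and it moves Visit 2 to Day 12.

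**Day 1 total = trial infusions + ambulance dose on the same calendar day**

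| Ambulance dose | Two infusions (first-half start) | One infusion (second-half start) |
|---|---|---|
| 200 mg | 1200 mg (at the maximum) | 700 mg |
| 250 mg | 1250 mg | 750 mg |
| 300 mg | 1300 mg | 800 mg |
| 400 mg | 1400 mg | 900 mg |
| 500 mg | 1500 mg | 1000 mg |

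The threshold is 1200 - 1000 = 200 mg with two infusions and 1200 - 500 = 700 mg with one. At the top of the assumed range the excess is 1500 - 1200 = 300 mg, or 300/1200 = 25%. After a second-half start the calendar-day total stays under the quoted maximum throughout that range.

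**Conflict within Section 2.2.** 4 x 500 mg = 2000 mg, against the 1200 mg maximum stated just before it.

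**Dilution of the primary comparison.** The plan's own figure reproduces: 2 x (1.6449 + 0.8416)² x 0.802² / (0.292 - 0.027)² = 113.26, so 114 per group and 228 completers; 228/0.75 = 304 randomised. Power at 114 per group is Φ[0.265/(0.802 x √(2/114)) - 1.6449] = 80.2%.

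Let f be the share of placebo patients exposed and r the share of the full-course effect carried by one dose, with no added benefit from that dose in Group I. The expected difference becomes 0.292 x (1 - f x r). Both f and r are assumptions.

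| r | f | Expected difference | Power |
|---|---|---|---|
| 0.05 | 0.25 | 0.2883 | 79.3% |
| 0.05 | 0.50 | 0.2847 | 78.3% |
| 0.05 | 1.00 | 0.2774 | 76.2% |
| 0.25 | 0.25 | 0.2737 | 75.1% |
| 0.25 | 0.50 | 0.2555 | 69.4% |

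For scale, a 500 mg dose is 500/10,000 = 5% of the parenteral course, and 500/(10,000 + 60 x 750) = 500/55,000 = 0.9% of the full course.

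**The case against.** The best defence is that several things must coincide: an ambulance dose above 200 mg, given on the same calendar day as the first infusion; a first-half start after consent, laboratory tests, ECG and eligibility review; and allocation to Group I. The documents give neither the usual ambulance dose nor the share of patients who receive one. The 1200 mg figure is a label limit quoted in Section 2.2, not a rule written for this trial, and the adjoining regimen contradicts it. All of this stands. It limits how often the excess could occur and rules out treating 1200 mg as the settled figure. It does not close the gap, because the rules as written permit the excess and nothing in either document prevents it.

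A reader might also infer more than the documents support:

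- **That the sponsor itself regards exposed placebo patients as effectively treated.** Section 2.3.2 says: "The use of Mexidol® at the pre-hospital stage with its subsequent administration in hospital allowed to significantly reduce mortality". The benefit is credited to pre-hospital dosing continued in hospital. Placebo patients have no continuation, and nothing is claimed there for a single dose alone.
- **That Section 2.4.2 is wrong to say that** "patients in the placebo group do not carry the risks associated with receiving the investigational therapy". The sentence goes on to give the reason, that the placebo components are inert. It concerns therapy given within the trial, and an ambulance dose is prior care. It needs no correction.
- **That sites cannot tell who was exposed.** Prior therapy is taken at Visit 0, so they can. What they cannot see is the allocation.
- **That the comparison is biased.** The exposure precedes 1:1 randomisation and is balanced in expectation. Baseline is scored the same way in both arms. The effect is dilution.

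**Conclusion.** The point holds. Criterion 26, the Day 1 schedule and the quoted daily maximum do not fit together: with two infusions on Day 1, any same-day ambulance dose above 200 mg takes a Group I patient past 1200 mg. The totals of 1200-1500 mg rest on assuming an ambulance dose of 200-500 mg and on counting by calendar day. How many patients this concerns is unknown. Section 2.2 is also inconsistent in itself (1200 mg against a regimen that reaches 2000 mg), so the passages need reconciling, and this review takes no view on which figure is right.

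The effect on the efficacy comparison is probably small. If one dose carried 5% of the full effect, power would fall from 80.2% to no lower than 76.2%, even with every placebo patient exposed. Larger losses need one dose to carry much of the benefit, and the documents give no evidence of that. This part justifies recording the exposure and one sensitivity analysis. It does not call the primary conclusion into question.

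**What to change.** 1. The sponsor should reconcile criterion 26 (Section 5.2 and synopsis), the Day 1 infusion schedule (Section 6.1 and Appendix 1) and the two dose statements in Section 2.2, and state how an ambulance dose counts towards Day 1. No dose or clinical rule is proposed here.
2. Make the dose, date and time of any pre-hospital administration of the substance a required field within the prior-therapy data already taken at Visit 0.
3. Add pre-hospital exposure (yes/no) by arm to the baseline tables in the SAP.
4. Pre-specify in the SAP one sensitivity analysis of the primary endpoint without exposed patients, in the same population as the main analysis. Exposure is fixed before randomisation, so leaving these patients out does not in itself break the randomised comparison. The analysis has fewer patients and should be read for its estimate and interval.

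The cost is amendment wording, one CRF field, one baseline table row and one sensitivity table. Depending on how the sponsor reconciles the passages, a few patients may start later or become ineligible.
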